6.2. Number of Subjects

Enough subjects will be screened and enrolled such that a total of approximately 20 total subjects will be recruited into the study. All subjects will receive all five test articles.

Subjects at screening will be given a sequential subject number starting with 1001, 1002, etc. Subject initials will be collected, but not used as an identifier. The subject number will be used to identify the subject and samples associated with each subject.

6.3. Study Endpoints

The primary objective of the study is to assess the humoral response of KeraStat Cream compared to the predicate devices utilizing the following endpoints:

- Size of wheal for the subject device and predicate devices at 15 minutes post SPT administration
- Size of wheal for the subject device and predicate devices at 6 hours and 1 – 2 days post SPT administration
- Safety of the subjects will be monitored and adverse events recorded throughout the duration of the study

6.4. Treatment Assignment

All subjects will receive all five test agents: KeraStat Cream, KeraStat Gel, Biafine, histamine, saline.

6.5. Criteria for Study Termination

Sponsor reserves the right to temporarily suspend or prematurely discontinue this study at any time for reasons including, but not limited to, safety or ethical issues or severe non-compliance. If Sponsor determines such action is needed, Sponsor will discuss this with the Investigator (including the reasons for taking such action) at that time. When feasible, Sponsor will provide advance notification to the Investigator of the impending action prior to it taking effect.

Study: KSCM-CRD-002 Version: 01	Effective Date: 17 Jul 19
--	--

Sponsor will promptly inform the Investigator and/or institution conducting the study if the study is suspended or terminated for safety reasons, and will also inform the regulatory authorities of the suspension or termination of the study and the reason(s) for the action. If required by applicable regulations, the Investigator or KeraNetics/KeraNetics designee, depending on whether the Institutional Review Board (IRB) is a central or local IRB, must inform the IRB promptly and provide the reason for the suspension or termination.

If the study is prematurely discontinued, all study data must be returned to Sponsor. In addition, arrangements will be made for all unused study device(s) to be destroyed or returned in accordance with the applicable procedures for the study.

7. SELECTION AND WITHDRAWAL OF SUBJECTS

7.1. Subject Inclusion Criteria

At the Screening Visit (Visit 1, day of the SPT), subjects must meet all of the following criteria:

1. Males or females aged 18 – 65 years.
2. Able to understand the informed consent, and provide written informed consent.
3. Healthy, unmarked skin at the test area (infrascapular regions of the back).
4. Agreement to avoid consumption of antihistamines until completion of the third test reading (Visit 2).

7.2. Subject Exclusion Criteria

To participate in the study, subjects must not meet any of the following criteria:

1. Women who are pregnant, lactating/nursing or plan to become pregnant.
2. Presence of skin disease, such as widespread urticaria or eczema.
3. Diagnosis of infectious disease.
4. Receiving corticosteroids, immunosuppressive agents, radiation or chemotherapy, topical growth factors, anxiolytics, imipramine, phenothiazine, dopamine, phenergen, clonidine, montelukast, immunotherapy, UV light therapy, H-2 antagonist, cyclosporine, or any other medication the investigator feels will affect the test within the last month.
5. Medical history of hypotension, severe hypertension, vasomotor instability, asthma, autoimmune disease, severe cardiac, pulmonary or renal disease.
6. Tattoo in the intrascapular test area.
7. History of surgical procedure/skin graft in the intrascapular test area.
8. Employee or relative of employee of KeraNetics.
9. Consumption of an antihistamine within seven days of study initiation.
10. History of hypersensitivity to histamine products.

Study: KSCM-CRD-002 Version: 01	Effective Date: 17 Jul 19
--	--

11. Any condition the investigator determines will compromise subject safety or prevent the subject from completing the study.
12. Participated in an investigational study within 30 days of the Screening Visit.

7.3. Subject Restrictions and Requirements

7.3.1. Medication and Therapy Restriction

See Section 8.2.

7.3.2. Food, Meals, Beverages and Fluid Intake

Subjects will be instructed to maintain their normal level of food and fluid consumption throughout the trial and therefore they should not alter their fluid intake greatly over the course of the trial. The testing center will provide the subject with a meal between the 15 minute and 6 hour evaluations on Day 1.

7.3.3. Contraception

Women of childbearing potential are defined as premenopausal women who are not surgically sterile. Surgically sterile is defined as women with tubal ligation, hysterectomy and/or bilateral oophorectomy.

Women of childbearing potential must:

1. Self-report that they are not pregnant or plan to become pregnant. This study does not require a negative urine pregnancy test.
2. Not be lactating.

Women of childbearing potential with male partners must:

1. Be willing to use acceptable methods of contraception from screening through follow-up unless the woman is in a monogamous relationship with a sterilized male partner (e.g., vasectomy).
2. Acceptable methods of birth control are systemic contraceptives (contraceptive pills, hormonal implants, contraceptive patches and injectable contraceptives), or intra-uterine devices), double-barrier methods, or as approved by the Investigator.

7.4. Subject Completion and Withdrawal

7.4.1. Subject Completion

A subject will be considered to have completed the study if they complete the entire study through the final evaluation (Day 2 – 3, Visit 2).

7.4.2. Patient Withdrawal (Premature Discontinuation from the Study)

A documented effort must be made to determine why a subject fails to return for the necessary visit or is dropped from the study, and the reason for withdrawal must be recorded in the source

Study: KSCM-CRD-002 Version: 01	Effective Date: 17 Jul 19
--	--

documents and case report form (CRF). A subject may withdraw or be removed from the study for any of the following reasons and will be treated as considered appropriate by the Investigator:

- Subject request (for any reason)
- In the opinion of the Investigator, continuation is not in the best interest of the subject.
- A serious or unexpected AE occurs such that continuation in the study is inappropriate.
- Test area (infrascapular region of the back) becomes marked or affected so that the Investigator is unable to read the test sites.
- Subject consumes antihistamines during the study.
- Pregnancy
- In the opinion of the Sponsor, continuation is not in the best interest of the subject.

If a subject is prematurely discontinued from participation in the study for any reason, the Investigator must follow up on all ongoing adverse events (if any).

In the event a subject is prematurely discontinued from the study due to an AE, or unexpected AE or serious adverse event (SAE) (as defined in Section 11.2.1), the procedures stated in Sections 11.2-11.6 must be followed.

7.4.3. Replacement of Patients

Subjects that fail the criteria for positive and negative controls in the triplicate re-administration will not be replaced.

8. TREATMENT OF SUBJECTS

8.1. Description of Subject Device

KeraStat® Cream is a non-sterile, non-implantable wound dressing intended to act as a protective covering and provide a moist environment in the management of a variety of partial thickness dermal wounds. KeraStat® Cream is provided in a screw top tube for multiple uses. Each tube contains 1 oz (29.6 mL) of KeraStat® Cream, which contains 5% keratin protein incorporated into a cream base.

The study device is described below in Table 3.

Study: KSCM-CRD-002	Effective Date:
Version: 01	17 Jul 19

Table 3: Subject Device

	Subject Device	Predicate Device	Predicate Device	Positive Control	Negative Control
Product Name	KeraStat Cream	KeraStat Gel	Biafine	Histamine	Saline
Manufacturer	KeraNetics	KeraNetics	Johnson and Johnson	HollisterStier, LLC	McKesson
Packaging	Multi-use tube	Single-use tube	Multi-use tube	Multi-use sterile amber vial with dropper	3ml Syringes
Components	5.0% keratin, purified water, glycerin, caprylic/capric triglyceride, dimethicone, mineral oil, sodium stearoyl glutamate, sodium polyacrylate/hydrogenated polydecene/trideceth-6, phenoxyethanol, ethylhexylglycerin, and sodium hydroxide	5.0% keratin; purified water, phenoxyethanol, carbomer, sodium hydroxide, and ethylhexylglycerin	Purified water, liquid paraffin, ethylene glycol monostearate, stearic acid, propylene glycol, paraffin wax, squalane, avocado oil, trolamine/sodium alginate, triethanolamine, cetyl palmitate, methylparaben (sodium salt), sorbic acid (potassium salt), propylparaben (sodium salt), and fragrance	6.0 mg/mL	0.9% NaCl
Route of Administration	Topical	Topical	Topical	Percutaneous	Percutaneous
Physical Description	White to tan cream	Hydrogel	White to tan cream	Clear liquid	Clear liquid

Study: KSCM-CRD-002 Version: 01	Effective Date: 17 Jul 19
--	--

8.2. Concomitant Medications and Therapies

8.2.1. Pharmacological Therapy

Concomitant medications are permitted during this study unless otherwise specified in the Exclusion Criteria.

8.3. Randomization

All subjects receive the same test agents in the same location (infrascapular region of the back) in the same order. The test agents will be administered going in descending order from a subject's head to feet: subject device, predicate device, positive control, and negative control.

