6. INVESTIGATIONAL PLAN

6.1. Overall Study Design

This is a single site, within subject, open-label comparison study to assess the humoral reaction KeraStat Cream compared to predicate devices. The length of study participation for a subject is two to three days depending on when a subject returns for their final follow-up evaluation. The Acceptable Study Windows is shown in Table 2.

Sufficient subjects will be screened such that 20 total subjects will complete the study. We expect excellent retention throughout the duration of the study, so we will target recruitment of 22 subjects. The sample size for the study is not based on any statistical considerations. A total of 20 subjects were deemed sufficient to assess the potential for a humoral response to KeraStat Cream compared to the predicate devices in support of establishing substantial equivalence.

Initial screening (Screening Visit; Visit 1) of the subject will take place the day of the SPT administration. The Screening Visit will include collecting demographic information, a brief medical history, and an abbreviated physical exam. If a subject fulfills all the inclusion criteria, none of the exclusion criteria, and gives their informed consent they will be admitted into the study.

The SPT will be performed on Day 1 (Visit 1), after screening and consent is obtained. The test will include five agents: the subject device (KeraStat Cream), predicate devices (KeraStat Gel, Biafine), positive control (histamine), and negative control (saline). The SPT will be administered on the infrascapular region of the back to the right of the midline. The region will be cleaned with alcohol wipes and allowed to air dry. Five marks will be made using a sterile skin marker to identify the test sites. These marks will be at least 4 cm apart and made in a

Study: KSCM-CRD-002	Effective Date:
Version: 01	17 Jul 19

vertical line. Once the marks are made, the back will be cleaned again with alcohol wipes and allowed to air dry. All subjects will initially receive the agents in the same order, going in descending order from a subjects' head to feet: subject device, predicate device (KeraStat Gel), predicate device (Biafine), positive control, and negative control.

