Each agent will be administered once using the UniTest® PC (Lincoln Diagnostics, Inc), following the manufacturer's instructions for use. In brief, all five agents are loaded into a well tray. A UniTest PC touch post is placed into a well, tip-down, to load an agent onto the touch post. Each well contains approximately 250-500 μ L. Allow the touch post to sit in the agent for at least 5 seconds. The touch post is removed and placed into contact at the appropriate mark for one second then pressed firmly into the skin. With proper pressure, all test sites should show a circular impression with an indented circle in the center surrounded by six dot indentations. A separate touch post is used for each agent. If blood is drawn, the test is repeated at an additional mark made along the vertical line. One minute after completing the pricks, absorbent tissue is applied to remove residual extract with care taken to avoid cross contamination of sites. When administration of the pricks is completed, the subject's shirt or a sheet will be used to cover the back and keep it warm. The subject will be instructed not to scratch the test area.

The initial evaluation of the sites will be taken after 15 (± 5) minutes following the final SPT administration in the series. When reading the test, the investigator will note the presence or absence of a wheal at all five sites and will measure the diameter of each wheal present. In order for the SPT to be valid the wheal at the positive site control must exceed that at the negative site control by 4 mm. If the above criteria are not met, the SPT will be repeated in triplicate on the infrascapular region of the back to left of the midline, following the same protocol. Three vertical lines will be made with all marks at least 4 cm apart. If the triplicate re-administration fails, the subject will be removed from the study.

Following the initial reading, the subject will remain at the testing facility. They will wait with the pricks covered by their shirt or a sheet for a period of approximately 6 hours. The subject will be instructed not to scratch the test area. During this time, the testing facility will provide a meal for the subject.

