9.5. Administration

During the SPT, the study device (KeraStat Cream) will be administered on the infrascapular region of the back to the right of the midline by qualified personnel. The region will be cleaned with alcohol wipes and allowed to air dry. Five marks will be made using a marker to identify the test sets. These marks will be at least 4 cm apart and made in a vertical line. Once the marks are made, the back will be cleaned again with alcohol wipes and allowed to air dry. All subjects

Study: KSCM-CRD-002	Effective Date:
Version: 01	17 Jul 19

will initially receive the agents in the same order, going in descending order from a subjects' head to feet: subject device, predicate devices, positive control, and negative control.

Each agent will be administered once using the UniTest® PC (Lincoln Diagnostics, Inc), according to procedures described herein. If blood is drawn, the test is repeated at an additional mark made along the vertical line. One minute after completing the pricks, absorbent tissue is applied to remove residual extract with care taken to avoid cross contamination of sites. When administration of the pricks is completed, the subject's shirt or a sheet will be used to cover the back and keep it warm. The subject will be instructed not to scratch the test area.

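### One fixed head-to-feet order for all subjects aliases agent with skin position and prick sequence in the Cream-versus-predicate comparison; a counterbalanced list would be a cheap improvement

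*Combined protocol and SAP*

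**What the plan says.** Section 8.3, headed Randomization, contains none: "All subjects receive the same test agents in the same location (infrascapular region of the back) in the same order". Section 6.1 gives the full head-to-feet sequence: "subject device, predicate device (KeraStat Gel), predicate device (Biafine), positive control, and negative control". Section 9.5 repeats that all subjects "receive the agents in the same order, going in descending order" from head to feet. Section 8.3 lists only one predicate in its sequence, so 6.1 is the only place that fixes the order of Gel and Biafine.

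Sections 6.1 and 9.5 say that subjects receive this order initially, but no other order appears. A site that bleeds is repeated at an extra mark on the same line. A failed control check leads to a triplicate retest on the left side under the same protocol. Neither step balances position.

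Other relevant details in section 6.1:
- Marks are at least 4 cm apart, and each agent has its own touch post.
- "One minute after completing the pricks, absorbent tissue is applied to remove residual extract".
- At each reading the investigator "will note the presence or absence of a wheal at all five sites", or at each site, so saline is always read.
- For a valid test, "the wheal at the positive site control must exceed that at the negative site control by 4 mm".

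The synopsis adds that a flare without a wheal does not count. Section 12.1 plans no formal statistics. Section 12.1.2 compares the proportion positive on Cream with that on the predicate.

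**The concern.** The study has one objective: the reaction to Cream compared with the predicates, within subject, in support of substantial equivalence. Wheal size at 15 minutes is the primary endpoint. Because no model or test is planned, the raw comparison has to carry the conclusion.

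Under one fixed order, Cream is always topmost and first pricked, Gel second and Biafine third. If skin reactivity varies along the back, or if place in the prick series matters, that effect is indistinguishable from a product effect on wheal size. It could create a difference or hide one. Adding subjects does not help, because every subject repeats the same pattern. The order has to be settled before anyone knows whether wheals will occur.

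**Working it through.** **Inputs.** Order and 4 cm minimum spacing: section 6.1. Twenty completers from about 22 enrolled: section 12.2. The documents give no position effect, wheal standard deviation or prick interval, so there is no figure of the plan's own to reproduce and no effect size is assumed.

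**1. Aliasing.** Write wheal = subject + agent + position. Separating all terms for 20 subjects needs 20 + 4 + 4 = 28 free parameters. Under the fixed order each agent indicator equals one position indicator, so the rank is 20 + 4 = 24. For n subjects it is n + 4 against n + 8 needed, so the gap never closes.

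**2. What a trend would do.** With a linear trend of t mm per position, the shift in a raw difference is t × (mean position of Cream − mean position of comparator).
- Fixed order: Cream minus Gel, (1 − 2)t, size 1t. Cream minus Biafine, (1 − 3)t, size 2t.
- Exactly balanced list: every agent has mean position (1+2+3+4+5)/5 = 3, so both shifts are 0.

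**3. Nearness to histamine.** Minimum distance is 4 cm × |position − 4|: Cream 12, Gel 8, Biafine 4, saline 4.

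**4. Contact before blotting.** Only if all sites are blotted together, which the protocol does not state, contact is 60 + (5 − position) × d seconds, with d the interval between pricks (assumed).

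| d | Cream | Gel | Biafine |
|---|---|---|---|
| 1 s | 64 s | 63 s | 62 s |
| 6 s | 84 s | 78 s | 72 s |
| 30 s | 180 s | 150 s | 120 s |

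**5. Alternatives at 20 subjects.** C = Cream, G = Gel, B = Biafine, H = histamine, S = saline.

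| List | Rank (of 28) | Times per position | Beside H, of 20 (C / G / B / S) | Mean distance to H, cm (C / G / B / S) |
|---|---|---|---|---|
| Fixed order | 24 | 20 or 0 | 0 / 0 / 20 / 20 | 12 / 8 / 4 / 4 |
| Five rotations × 4 | 28 | 4 | 0 / 0 / 16 / 16 | 9.6 / 9.6 / 6.4 / 6.4 |
| 20-line list | 28 | 4 | 8 / 8 / 8 / 8 | 8.0 for all |

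The 20-line list is ten Williams orders, then the same ten with C and B swapped and G and S swapped:
- Lines 1–10: CGSBH, GBCHS, BHGSC, HSBCG, SCHGB, HBSGC, SHCBG, CSGHB, GCBSH, BGHCS
- Lines 11–20: BSGCH, SCBHG, CHSGB, HGCBS, GBHSC, HCGSB, GHBCS, BGSHC, SBCGH, CSHBG

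All 20 lines differ, and each ordered neighbour pair occurs 4 times.

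**6. With 22 enrolled and losses.** Subjects 21 and 22 reuse lines 1 and 2. Over those two lines the positions sum to 1 + 3 = 4 for Cream, 2 + 1 = 3 for Gel and 4 + 2 = 6 for Biafine. The shifts are (4 − 3)/22 = 0.05t and (4 − 6)/22 = −0.09t. Over all 231 ways of losing 2 of 22, the rank stays 28 and the largest shifts are:
- Cream minus Gel, 0.4t: lose SCBHG (difference −3) and CSHBG (−4); (1 + 7)/20.
- Cream minus Biafine, 0.5t in size: lose BHGSC (+4) and BGSHC (+4); (−2 − 8)/20.

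**7. When to assign.** Section 6.2 states: "Subjects at screening will be given a sequential subject number starting with 1001, 1002, etc". Section 6.1 admits a subject only later, once a person who meets the criteria "gives their informed consent they will be admitted into the study". Orders tied to the screening number would be lost with each screen failure. In 20,000 simulated runs, exact position balance in the first 20 enrolled survived in about 14%, 1.6% and 0.2% at assumed failure rates of 10%, 20% and 30% (the documents give none). Assigned in order of enrolment, it is exact at any rate.

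**The case against.** The strongest reply is that no position, sequence or spread effect appears anywhere in the documents, that the study is descriptive, and that an earlier patch test on intact skin saw no adverse skin reactions in 50 subjects. If no device site shows a wheal, order hardly matters, and Cream's own count against the 3 mm criterion does not depend on the comparison. All of this stands. It limits the point to a cheap improvement. It does not remove the aliasing.

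The spacing, separate touch posts, careful blotting and flare rule also limit spread from histamine. Saline, which is as close to histamine as Biafine is, gives a partial check on spread and on reaction to pricking itself. That stands too, but saline is always last on the line and so says nothing about position.

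Four stronger readings are tempting and are not supported:
- *The fixed order biases the comparison, perhaps in Cream's favour.* The documents support no size and no direction.
- *Cream necessarily has the longest contact time.* That depends on blotting all sites together, which is not stated. With a 1-second interval Cream and Gel would differ by 1 second.
- *A Cream wheal would be uninterpretable.* A wheal of 3 mm or more at Cream with none at saline is hard to attribute to spread or to pricking alone. What stays ambiguous is how far position contributes to a difference in wheal size.
- *Counterbalancing removes the problem entirely.* The shift is exactly 0 only at exact balance, and the study remains open-label.

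The remedy also has a real hazard. Table 3 gives Cream and Biafine the same physical description, so a swap between them would be hard to see and would misattribute a reaction.

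**Conclusion.** The point holds as a cheap improvement. Agent and position are fully aliased (rank 24 of 28 at 20 subjects), and the gap does not close with more subjects. Under an assumed linear trend of t mm per position, the exposure is 1t for Cream minus Gel and 2t for Cream minus Biafine. It falls to 0 at exact balance, and to at most about 0.4t and 0.5t if any 2 of 22 enrolled are lost from the 20-line list. The value of t is unknown and may be zero. The aliasing follows from the protocol text alone. The shifts rest on the linear form, and the distances on the 4 cm minimum spacing. The practical consequence is confined to the case where device sites do produce wheals.

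**What to change.** In sections 6.1, 8.3 and 9.5, replace the single order with wording such as: *Agents are applied head to feet in the order on the next unused line of a prespecified counterbalanced list, taken in order of enrolment after eligibility is confirmed and not by screening number. Subjects after the 20th restart the list.* Name both predicates consistently in all three sections.

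- **Minimum list:** the five rotations of the current order, each used 4 times. This balances position but not nearness to histamine.
- **Preferred list:** the 20 lines above, which also balance neighbours and mean distance to histamine.
- Record the position-agent map and any extra mark after a bleed on the CRF. Use the subject's own order on all three lines of any triplicate retest.
- Label the wells against the subject's list line, to guard against a Cream/Biafine swap.
- In section 12.1.2, add one descriptive table of wheal size and positive count by position. State that balance is exact only at 20 subjects on the full list.

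**Cost:** a one-page list, well labels, one CRF field and one table, with no extra subjects, visits or staff. **Downsides:** the risk of misplacing an agent rises. With the preferred list, Cream is beside histamine in 8 of 20 subjects instead of 0, and saline in 8 instead of 20, so saline's check on spread is available in fewer subjects. The two control sites used for the 4 mm validity check also change place between subjects. The change does not address open-label reading.
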